Aerobes	Fresh	2.53E+05	1.76E+05
	1 freeze-thaw	4.30E+05	4.43E+05
Anaerobes	Fresh	5.80E+07	3.96E+07
	1 freeze-thaw	6.20E+07	5.29E+06

CFUs per mL of Capsules G3 Microbial Emulsion Matrix

_CFUs per mL of stool homogenized 1:1 (w/v) with buffer containing 12.5% glycerol and 0.9% saline, after one freeze-thaw cycle

	per mL
Aerobes	4.53E+06
Anaerobes	1.47E+09
Spores	2.00E+06

These concentrations will be used for the upcoming trial to ensure that the material concentrations in our older trials are expanded.

- We anticipate providing 5 capsules at a time for the oral FMT and 60ml of the FMT enema.
- The placebo for the oral FMT will be made using identical capsules as the active drug, except it will contain 10%/weight trehalose (the cryoprotectant used in preparation of freeze-dried microbiota) and the rest carboxymethylcellulose. Since the capsules are not transparent and have no specific smell or taste, there should be no difficulty in maintaining double blinding.
- The placebo for the liquid formulation is non-bacteriostatic, sterile phosphate buffered saline containing 10% USP grade glycerol. Each dose will be packaged in individual cryobags, just as the active drug.

Study Design

Overall objective: To determine the effect of dual oral and rectal administration of FMT from a rational donor on clinical outcomes (hospitalizations, brain function, quality of life) and host-microbiota interactions (microbial composition and bile acid composition with systemic and intestinal inflammation), compared to single route of administration and placebo, along with a second oral capsular FMT vs placebo administration in patients with cirrhosis and HE using a randomized, phase II clinical trial.

Design overview:

Four groups of outpatients with cirrhosis will be randomized using random sequence generator into placebo and FMT groups and followed for 6 months under an FDA IND double-blind clinical trial.

Group 1: Dual oral and rectal FMT, Group 2: Oral FMT and rectal placebo, Group 3: Oral placebo and rectal FMT and Group 4: Oral and rectal placebo

A repeat oral capsular FMT vs placebo based on the group assignments above will be provided to every subject in at day 30.

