3. The following will be recorded in all interventions (dose, Unit ID/Lot# of each treatment, Expiration Date and storage condition)

Number of interventions: One administration of rectal placebo or FMT and two administrations of oral FMT or placebo

We will ensure that each subject receiving active FMT will receive material (oral/rectal) from the same donor.

Duration of Follow-up after FMT: 6 months

Samples collected at baseline (before FMT), and at the visits specified above will be:

- a. Stool (microbiome, bile acid profile, metagenomics, metabolomics)
- Blood (CBC, Basic metabolic panel, LFTs, INR, endotoxin, and storage for circulating microbiome, systemic inflammatory markers, bile acids and metabolomics)
- c. Urine for metabolomics

Sample processing will be done using standard precautions at the McGuire VA Medical Center and samples will be stored for analysis of the secondary endpoints. Microbiota analysis will be performed at George Mason University and University of Minnesota, and metabolomics will be performed at the UC Davis NIH West Coast Metabolomics Center or Metabolon. We will perform the bile acid analysis at the McGuire VA Medical Center laboratories. Additional analyses at the Institute of Hepatology, London, UK, and the University of North Carolina at Chapel Hill. We may also use other referral laboratories as needed.

Statistical analysis: These will be performed using ANOVA of delta changes after intervention/follow-up using Chi-square and Fisher exact for non-parametric (hospitalizations, HE episodes, covert hepatic encephalopathy etc.), for continuous variables, and specialized bio-informatics analyses for the microbiota (see details below). These will be adjusted for age, gender, MELD score and alcoholic etiology of cirrhosis.

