Sample size: Based on the published study with rectal FMT¹⁰, we found that standard of care patients had an 80% chance of hospitalization at 6 months, while FMT had a 20% hospitalization rate. Given that we had used antibiotics for this study, we will assume that rectal FMT alone will have a 30% chance of hospitalization rate without antibiotics. We will also assume that oral FMT alone will have a similar hospitalization rate, and their combination will have a 10% hospitalization rate. Using a significance level of α =0.05, a sample size of 25 per group will provide a power of 100% between groups, 20 per group will give a power of 98% to define differences between the groups, while a sample size of 15 patients per group will give a power of 94% between the groups. Therefore, we will enroll 100 patients (25 in each group) for this trial. This sample size calculation will also be valid when we include the second oral FMT with a sample of 10 per group giving 88% power, 15 per group giving 97% power and 25 giving 99% power.

Specialized analyses:

Inflammatory milieu: We will perform the analysis for endotoxemia using the validated Limulus amebocyte lysate (LAL) assay and serum inflammatory cytokines (IL-6, TNF, IL-1b) using ELISA at [name] and [name]'s laboratory at the McGuire VAMC or at Assaygate¹⁴.

Microbial Analysis: Bacterial community composition in stool will be characterized using OTU counts generated as described above. OTU counts will be converted to measures of relative abundance to account for variation in sequencing coverage between samples and compared to the donor sequence. Statistical analysis will be carried out using the statistical software package R. Alpha (α) diversity (richness and evenness of taxa within a population) will be reported using the Shannon Index¹⁵ and Chao1 richness estimator¹⁶. Changes in abundance of individual taxa will also be analyzed using traditional univariate statistical methods. We will use LEfSe (Linear discriminant analysis Effect Size) to determine the features most likely to explain differences. All comparisons will be performed between treatment arms, to gauge donor engraftment in the three FMT-assigned arms, as well as within groups to compare to their baseline microbial composition¹⁷. These will be performed at George Mason University and University of Minnesota. Functional analysis using bile acids, SCFA and metabolomics will also be performed.

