- 1. Safety-related (at 6 months): Liver-related hospitalizations, other serious adverse events (SAE) and adverse events related to interventions.
- 2. Microbiota composition: Stool 16SrRNA sequencing and engraftment of donor into recipients.
- Inflammatory milieu: Endotoxemia (LAL), Systemic inflammatory cytokines (IL-6, TNF, IL-1b using ELISA)
- 4. Bile acid profile and gut-liver mediators expression: Bile acid profile using LC/MS in stool and serum and serum C4 (7α-Hydroxy-4-cholesten-3-one).
- 5. Urinary metabolomics to evaluate gut-microbial markers
- 6. Brain function: Two validated testing strategies, PHES and EncephalApp Stroop Test, and Quality of Life: Sickness Impact Profile (a validated profile for healthrelated quality of life in cirrhosis)

Adjudication: Data and safety monitoring for this study will be provided by the Clinical Science Research & Development (CSR&D) centralized Data Monitoring Committee (DMC). The DMC is provided by CSR&D to ensure independent oversight of the safety and integrity of the project. The DMC is an independent multidisciplinary group, whose members have collectively – through research, education, training, experience, and expertise – the requisite knowledge pertinent to the subject areas to be reviewed. Membership details are available on the CSRD website. The DMC will provide an ongoing independent evaluation of this study focused on safety and feasibility, including participant accrual and retention, adverse events monitoring, and data analyses. Meetings will be held three times per year at which recommendations will range from approval to continue (unconditionally or with conditions to be addressed) to probation or possibly termination, if there are problems with enrollment or safety concerns

All outcomes will be compared between groups as well as post-intervention to baseline.

Visits at VCU and VAMC:

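### The four-arm 2x2 trial has no rule for its pairwise comparisons, and the stated power between groups does not apply to dual versus single route

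*Combined protocol and SAP*

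**What the plan says.** Under Study Design, the design overview states: "Four groups of outpatients with cirrhosis will be randomized using random sequence generator into placebo and FMT groups". The groups are dual FMT, oral FMT with rectal placebo, oral placebo with rectal FMT, and double placebo, allocated 1:1:1:1. That is a 2x2 crossing of route by active or placebo. The overall objective names the comparison of dual administration with single-route administration and with placebo.

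The Statistical analysis paragraph reads: "These will be performed using ANOVA of delta changes after intervention/follow-up using Chi-square and Fisher exact for non-parametric". It then adjusts for four baseline covariates (age, gender, MELD and an alcohol-related cause). Endpoints and Plan of Analysis adds: "All outcomes will be compared between groups as well as post-intervention to baseline". Neither place gives a route effect, an interaction, a list or order of contrasts, or a multiplicity rule.

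The Sample size paragraph works on 6-month hospitalization. It claims power between groups of 100%, 98% and 94% at 25, 20 and 15 per group, without saying which groups are compared.

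**The concern.** The objective cannot be met by one overall test. A significant four-group result says that the arms differ somewhere; it does not say that two routes beat one. Pairwise tests must therefore follow, and the plan does not say which ones or at what level. Two things are at stake. With no rule, the error rate for pairwise claims is not held at the stated 0.05. And a reader of the Sample size paragraph would take dual v single to be fully powered, when it is the weakest contrast in the design.

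**Working it through.** **Inputs, all from the Sample size paragraph.** "Using a significance level of α =0.05" (two-sided assumed, as sidedness is not given). Double placebo 80%: "standard of care patients had an 80% chance of hospitalization at 6 months". Rectal alone 30%: "rectal FMT alone will have a 30% chance of hospitalization rate without antibiotics". Oral alone taken as 30%: "We will also assume that oral FMT alone will have a similar hospitalization rate". Dual 10%: "their combination will have a 10% hospitalization rate". There are 25 per group, with no dropout allowance.

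**1. Reproduce the stated power.** For a four-group chi-square test the mean rate is (10+30+30+80)/4 = 37.5%. The squared deviations sum to 0.0756 + 0.0056 + 0.0056 + 0.1806 = 0.2675 (before rounding of the terms). The noncentrality is n × 0.2675/(0.375 × 0.625) = 1.141n, that is 28.5, 22.8 and 17.1 at n = 25, 20 and 15. On 3 degrees of freedom the power is 0.9975, 0.988 and 0.949, against the stated 1.00, 0.98 and 0.94. A two-group comparison of 80% v 20% also fits (0.998, 0.989, 0.951). Single v placebo, 80% v 30%, does not (0.967, 0.921, 0.820).

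**2. Dual v single, 10% v 30%, n = 25.** Power = Φ{[|p1−p2|√n − 1.96√(2p̄q̄)] / √(p1q1+p2q2)}, with p̄ = 0.20.

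- |p1−p2|√n = 0.20 × 5 = 1.000
- 1.96 × √0.32 = 1.109
- √(0.21+0.09) = 0.548
- Φ[(1.000 − 1.109)/0.548] = Φ(−0.199) = 42%

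Simulated Pearson power is 45% and Fisher power is 31%. The chance that dual is significantly better than both single-route arms is 28-29% (Pearson) or 16-17% (Fisher). For 80% power, n = (1.109 + 0.842 × 0.548)²/0.20² ≈ 62 per arm.

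**3. False positives over six pairs.** Four arms give 4 × 3/2 = 6 pairs. If the pairs were independent, the chance of at least one false positive would be 1 − 0.95⁶ = 26.5%. The pairs share arms, so this was simulated with 25 per group and all arms equal:

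| Common rate | Chi-square | Fisher |
|---|---|---|
| 30% | 20.7% | 9.9% |
| 50% | 25.4% | 14.1% |
| 80% | 21.4% | 10.1% |

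The four-group test alone stays near 5%.

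**4. Is a four-group gate enough?** With all arms equal, gating the pairs on that test gives about 5%, with essentially no power loss at the planning rates. It fails when only some arms are equal. At 80/30/30/30 (placebo first, the three FMT arms alike) the gate opens in 98% of trials, and a false positive among the three FMT pairs still occurs in about 13% (chi-square) or 6% (Fisher). A three-group test before each pair closes that gap. If only one route works, the arms form two equal pairs. Two independent tests at a true 0.05 then give 1 − 0.95² = 9.75%, so full closure also needs a joint test of the two disjoint pairs.

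**5. Route main effects.** The margins are (10+30)/2 = 20% with a route and (30+80)/2 = 55% without it, 50 v 50. A Mantel-Haenszel test of oral stratified by rectal has 98% power at 0.05 and 96% at 0.025. At 80/30/30/30, where dual adds nothing over single, it is still significant in 76% of trials at 0.05. The planned rates imply these effects:

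| Scale | Route alone | Added to the other route |
|---|---|---|
| Risk difference | 30 − 80 = −50 points | 10 − 30 = −20 points |
| Odds ratio | (0.3/0.7)/(0.8/0.2) = 0.11 | (0.1/0.9)/(0.3/0.7) = 0.26 |
| Risk ratio | 30/80 = 0.375 | 10/30 = 0.333 |

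Only the risk ratio is nearly constant. Power to detect the interaction is 45% on the risk-difference scale and 13% on the log-odds scale.

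**The case against.** The strongest reply is that the plan never commits to six tests at 0.05. It names ANOVA, which is normally an overall test, and the stated power matches a four-group chi-square. On that reading the error is about 5% per endpoint and the power figures are sound. This stands as far as it goes: the six-pair error rate is conditional, and the stated power is not an arithmetic mistake. It does not remove the point, because the objective needs contrasts that an overall test cannot supply.

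A reader might also infer that comparing all groups is what leaves dual v single underpowered, and that a factorial analysis would rescue it. The documents do not support this. The low power comes from 25 per arm and the assumed 10% v 30%. A main effect answers a different question, the average effect of a route, so 98% against 31-45% is not like for like. The same applies to continuous outcomes, where the detectable difference at 80% power is 0.57 SD for 50 v 50 and 0.81 SD for 25 v 25. Making the factorial model the main analysis is a debatable trade-off that the 76% figure weakens.

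Finally, all the power figures concern hospitalization. The primary endpoint is FMT-related serious adverse events including HE recurrence, for which no rate is given, so they do not carry over to it.

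**Conclusion.** The point holds in this form: the objective requires dual v single and v placebo contrasts, and the plan gives no rule for them. If all six pairs are tested at 0.05, the familywise error per event endpoint is 21-25% (chi-square) or 10-14% (Fisher) when all arms are equal. Dual v single has about 31-45% power on hospitalization, whatever the stated 100% suggests. This rests on two-sided tests, an oral rate equal to the rectal rate, and no dropout; any dropout lowers the power further. The plan is unadjusted only in the multiplicity sense, since covariate adjustment is specified. Multiplicity across the many endpoints and the comparisons with baseline remains under any reading and is not solved by a rule within each endpoint.

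**What to change.** 1. For each outcome, run the four-group test first. Make a pairwise claim only by closed testing: the four-group test, every three-group test containing the pair, the joint test of that pair with the other two arms, then the pair itself (Fisher for events).
2. Name dual v single as a separate contrast, report it with a confidence interval, and state its power in the Sample size paragraph. Say there that the 100% refers to the four-group test, if that is what was calculated.
3. As pre-specified supporting analyses, report the oral and rectal main effects, each stratified by the other route and tested at 0.025, with the interaction estimate and the four cell results. Keep the planned covariates in the models. These do not replace the cell contrasts.

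The cost is wording in the analysis plan and some pairwise power at the planning rates. Single v placebo falls from about 95% to 91% (Fisher), and dual v single from about 45% to 33% (Pearson). With Fisher, dual v single starts from 31% and can only fall. Arms, allocation and patient numbers are unchanged. Powering dual v single directly would need about 62 per arm, which is a different trial.

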The primary aim is: To evaluate the safety and tolerability of fecal transplant through rectal and oral capsular routes in cirrhosis and HE from a liver disease and symptom standpoint using analysis of serious adverse events, especially HE recurrence, in a placebo-controlled trial.

Secondary aims are between the groups:

- 1. Safety and tolerability of FMT compared to placebo
 - a. Frequency, severity and relatedness of solicited and unsolicited AEs through day 30
 - b. Occurrence of new potentially transmitted infections through six-months post FMT
 - c. Occurrence of new onset or significant worsening of chronic medical conditions post-FMT
- 2. To define the changes in microbiota composition and function of the stool microbiota after FMT compared to pre-FMT baseline and donor compared to placebo

- 3. To evaluate changes in systemic inflammatory cytokines and endotoxin, quality of life and cognitive function compared to pre-FMT baseline and compared to placebo
- 4. To determine occurrence of new onset or significant worsening of chronic medical conditions through six months post-FMT and compared to placebo
- 5. To evaluate the changes in the microbiota after the second oral FMT vs. placebo compared to baseline values

Inclusion/Exclusion Criteria:

Inclusion criteria:

- A. Cirrhosis diagnosed by either of the following in a patient with chronic liver disease
 - a. Liver Biopsy
 - b. Radiologic evidence of varices, cirrhosis or portal hypertension
 - c. Laboratory evidence of platelet count <100,000 or AST/ALT ratio>1
 - d. Endoscopic evidence of varices or portal gastropathy
 - e. Fibroscan values suggestive of cirrhosis
- B. On treatment for hepatic encephalopathy (patient can be on lactulose and rifaximin)
- C. Age: at least 21 years of age
- D. Able to give written, informed consent (demonstrated by mini-mental status exam>25 at the time of consenting)
- E. Women of child bearing potential must agree to use effective contraception for the duration of the study and for 10 days prior and 30 days after the study
- F. Negative pregnancy test in women of childbearing age

Exclusion criteria:

- A. MELD score >22
- B. WBC count <1000 cells/mm3
- C. Platelet count < 25,000/mm3
- D. TIPS in place for less than a month
- E. Currently on antibiotics apart from rifaximin
- F. Infection at the time of the FMT (diagnosed by blood culture positivity, urinalysis, paracentesis as needed)

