Dosage: FMT Procedure #1 5 FMT capsules or 5 placebo capsules and 60 ml FMT enema vs 60 ml placebo FMT Procedure #2 5 FMT capsules or 5 placebo capsules

Route of Administration: Oral and enema for baseline, and oral only for Day 30

Timing of administration: Twice (at baseline and Day 30)

Procedures:

Once patients are randomized 1:1:1:1 into Group 1: Dual oral and rectal FMT, Group 2: Oral FMT and rectal placebo, Group 3: Oral placebo and Rectal FMT and Group 4: Oral and rectal placebo, both will be followed over 6 months with intensive follow-up in the first 30 days.

At the end of one month, we will provide another oral-route FMT or placebo to all subjects based on their initial assignment (Groups 1 and 2 will get oral FMT 5 capsules again, and Groups 3 and 4 will get 5 capsules of placebo again). All subjects will be followed with monthly visits till 6 months to assess SAEs.

An overview is shown below in Figure 1 (extended through 6 months)

Procedures:

Visit 1: After initial review of the medical record is completed and informed consent is obtained, potentially eligible patients will be interviewed and their questions about the study will be answered by the study team. Vital signs (including heart rate, blood pressure, respiratory rate, temperature) and weight will be measured. Physical exam will be performed. We will administer the Mini-mental status exam (MMSE)^{13 4}. For those <25, we will deem them not able to give consent and their clinicians will be notified. For the rest we will obtain blood and urine for further confirming eligibility (MELD score and complete blood count for platelet count/ANC). Patients will also be administered a safety test capsule orally to ensure they can swallow it without any issues. If the subject is eligible and can swallow the capsules and otherwise fits criteria, they will be randomized into one of the four groups (Groups 1-4, Table 2) and a date for visit 2 will be generated. A dietary recall will be performed and the patients will be asked to stay on the same diet throughout the trial. We will perform the validated lactulose/mannitol testing at baseline. Patients will undergo brain function tests and quality of life assessment during this visit to establish their baseline. Patients will be given a Stool Collection Kit to bring in the day of the baseline visit (Visit 2). They will also be given a symptom diary and instructions to complete it.

Table 2: Patient Groups

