1. Study procedure-related adverse events from enema (e.g. perforation, bleeding, etc.)

- 2. FMT material-related adverse events (e.g. transmissible infection, allergic reaction)
- 3. Capsule ingestion-related adverse events (pill-associated dysphagia)

4. Short-term safety: Both solicited and unsolicited adverse events will be recorded by, clinical assessment at all in-person visits. The subjects will have the ability to telephone the study team at any point during the study.

5. Long-term safety: follow-up monthly till 6 months to evaluate for SAEs (listed below).

Solicited AEs throughout the trial will be

- (a) fever:
- (b) diarrhea
- (c) vomiting
- (d) constipation
- (e) GI bleeding
- (f) abdominal cramping and pain
- (g) Development of HE (confusion/altered mental status):
- (h) Development of infections, specifically spontaneous bacterial peritonitis
- (i) New onset or significant worsening of chronic medical conditions
- (j) New potentially transmitted infections

We do not expect the infections to occur at a higher rate than the natural history of cirrhosis at this stage. This is borne out by our enema study, in which the FMT group had no infections. Also, a nasojejunal study performed by Phillip et al in severe alcoholic hepatitis, whose MELD scores were much higher than our proposed patients, did not reveal a poor safety profile. We will monitor for all infections and specifically for spontaneous bacterial peritonitis (SBP).

All safety assessments in FMT will be compared to placebo groups given the advanced nature of the cirrhosis and the association of several of these symptoms in the natural history of the disease

Stop-points or reportable adverse events

Any hospitalization or event that is life-threatening will be deemed a serious adverse event in the FMT group and reported to the IRB, FDA, DMC and Molecular and Cellular Therapeutics (GMP) facility at the University of Minnesota within 72 hours (per usual protocol).

This will include the development of an infection that is gut-based/not gut-based:

Gut-Related

- Spontaneous Bacterial peritonitis
- Infectious diarrheal illnesses

Others

- UTI
- Respiratory
- Skin/soft-tissue
- Bacteremia

Overall Study Halting Rules

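### The primary safety comparison with placebo rests on tests of difference, with no interval or upper limit to describe excess harm

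*Combined protocol and SAP*

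**What the plan says.** The primary aim, under Study Design, is "To evaluate the safety and tolerability of fecal transplant through rectal and oral capsular routes in cirrhosis and HE", by analysis of serious adverse events (SAEs), especially recurrence of hepatic encephalopathy (HE), in a placebo-controlled trial. Endpoints and Plan of Analysis gives the primary endpoint as FMT-related SAEs including HE recurrence within 6 months, and says that all outcomes will be compared between groups.

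The text after the list of solicited adverse events adds: "All safety assessments in FMT will be compared to placebo groups given the advanced nature of the cirrhosis". The Statistical analysis paragraph names the method for events: "using Chi-square and Fisher exact for non-parametric (hospitalizations, HE episodes, covert hepatic encephalopathy etc". Safety and hospitalization analysis says that non-serious events will be compiled to show trends between groups.

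The Sample size paragraph says "we will enroll 100 patients (25 in each group) for this trial", and Procedures says "Once patients are randomized 1:1:1:1". Its power statement, "Using a significance level of α =0.05, a sample size of 25 per group will provide a power of 100% between groups", concerns a fall in hospitalization. No power is given for detecting harm.

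Safety is also handled outside these tests. The DMC votes on relatedness (Safety and hospitalization analysis; Assessment of Causality). Overall Study Halting Rules trigger a safety review on counts of related events. There are also individual halting rules.

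**The concern.** A chi-square or Fisher test has 'no difference' as its null hypothesis. A significant excess would show harm, but a non-significant result does not show that harm is absent or small. The plan does not say how large an excess the data would have to rule out, or that any limit on the excess will be reported. Its primary aim therefore has no stated route from the data to a safety statement.

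Two background passages show how a null result could be over-read. On infections not exceeding the natural history of cirrhosis, the protocol says: "This is borne out by our enema study, in which the FMT group had no infections". That group had 10 patients. The section on the team's capsule experience reports no safety signal against placebo at 10 v 10, under a statement that the oral route is safe. If the final report reasoned in the same way, the main conclusion would be weakest in the direction that matters most to patients.

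**Working it through.** **Inputs.** From the documents: α=0.05, 25 per group, four groups allocated equally. That gives 25 v 25 for one FMT arm against placebo, or 75 v 25 if the three FMT arms are pooled. Sidedness is not stated; I assume two-sided. No placebo rate is given for SAEs overall, HE recurrence or infections, so 5% to 30% is an assumption. The one rate given is 80% hospitalization at 6 months under standard of care.

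**The plan's own power.** The stated figures are 100%, 98% and 94% at 25, 20 and 15 per group. Take an overall four-group chi-square test with hospitalization rates 80%, 30%, 30% and 10%. The mean rate is 0.375. The noncentrality is n × Σ(p − 0.375)² / (0.375 × 0.625) = n × 0.2675 / 0.2344. At n=25 this is 28.5 on 3 degrees of freedom, giving power of 99.7%. At n=20 and n=15 the power is 98.8% and 94.9%. The stated figures reproduce to within 2 points, but they describe an overall test for benefit and do not carry over to harm.

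**Chance of missing a true harm.** For rates p1 (FMT) and p0 (placebo), sum Bin(a; n1, p1) × Bin(b; n0, p0) over all tables with p≤0.05 and a higher rate on FMT, and subtract from 1.

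| True rates, placebo to FMT | Fisher, 25 v 25 | Uncorrected chi-square, 25 v 25 | Fisher, 75 v 25 |
|---|---|---|---|
| 5% to 15% | 93% | 79% | 86% |
| 10% to 25% | 82% | 70% | 71% |
| 20% to 40% | 77% | 65% | 59% |
| 30% to 50% | 77% | 67% | 63% |
| 20% to 50% | 49% | 36% | 25% |
| 30% to 60% | 49% | 38% | 30% |

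The first four rows are the 10- to 20-point cases. A 20-point excess from a lower base is missed less often by Fisher: 5% to 25% in 63% of trials (41% pooled), and 10% to 30% in about 70% (about 50% pooled).

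For hospitalization at the documents' 80%, swapping events and non-events turns 80% to 90% into 20% v 10%. Fisher power at 25 v 25 is then 9%, so about 91% of trials miss it.

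**What an interval would add.** Suppose SAEs occur in 30/75 on FMT and 5/25 on placebo (40% v 20%). Fisher gives p=0.091. The Wilson limits are 29.7% to 51.3% and 8.9% to 39.1%. The Newcombe limits for the excess are
- lower: 0.20 − √[(0.400 − 0.297)² + (0.391 − 0.200)²] = −0.017
- upper: 0.20 + √[(0.513 − 0.400)² + (0.200 − 0.089)²] = 0.359

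The data are compatible with anything from 2 points fewer to 36 points more, which the p-value does not show.

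**Zero events.** The exact two-sided 95% upper limit is 1 − 0.025^(1/n): 30.8% for n=10, 13.7% for n=25 and 4.8% for n=75. The 0/10 infections in the enema study are compatible with a true rate of up to 31%.

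**The case against.** A reader might infer three stronger things that the documents do not support.

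- **That safety is judged only by these tests.** It is not. The primary endpoint depends on relatedness, the DMC votes on it, and a single related transmitted infection or a single serious, unexpected, related event triggers a review. These rules need no p-value. They are monitoring rules, however, and set no end-of-trial criterion against placebo.
- **That p>0.05 will be reported as safe.** No section says so. The sentence on infections is background about expected risk. It is accompanied by a second study and followed by a commitment to monitor all infections. Over-reading is plausible but not planned.
- **That a doubling or tripling of harm would usually be missed.** This fails at higher base rates. Fisher misses 20% to 60% in 21% of trials (6% pooled), 15% to 45% in 47% (21% pooled) and 30% to 60% in 49% (30% pooled). Nor can an 80% hospitalization rate double.

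The plan also names chi-square, which misses fewer harms than Fisher, as the table shows. Low power for moderate harm is inherent in 25 per arm in phase II, and intervals do not change that. They could also be calculated at reporting without a prior plan. All of this stands, and it limits the point to how the safety conclusion is drawn. It does not supply the missing interval or criterion, and a small trial has more need of one.

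**Conclusion.** The point holds in a limited form. Monitoring rules aside, the plan's only inference on events for its primary safety aim is a test of difference, with nothing to bound the excess over placebo. That a non-significant result cannot by itself support a safety conclusion does not depend on the assumed rates. The miss rates do: they assume the placebo rates shown, a two-sided 0.05 level, full follow-up of all 100 patients and, for the larger figures, Fisher's test. The documents define no relevant excess, so it cannot be said that most relevant harms would be missed. This is a worthwhile, low-cost improvement to the analysis text and does not invalidate the design.

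**What to change.** In the Statistical analysis paragraph, for all-cause SAEs, HE recurrence, infections and unplanned hospitalization:

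- Make the risk difference with a 95% confidence interval (Newcombe or Miettinen-Nurminen) the basis for the safety conclusion, for pooled FMT v placebo (75 v 25) and for each FMT arm v placebo (25 v 25).
- Report exact 95% upper limits for events not seen on FMT: 4.8% for 0/75 and 13.7% for 0/25.
- State that safety will be described by the upper limit of the interval, so that only excesses above it count as excluded, and that p>0.05 will not be reported as evidence of no added harm.

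No formal margin is proposed. With equal true rates of 10%, a 10-point margin, one-sided 0.025 and 80% power, the requirement would be (1.96 + 0.842)² × 2 × 0.10 × 0.90 / 0.10² = 142 per arm.

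The change needs no new data or patients. The cost is a more cautious statement, because the limits will be wide. With equal rates of 20%, the approximate half-width is 1.96 × √(0.20 × 0.80 × (1/25 + 1/25)) = 22 points per arm, and 18 points pooled with 1/75 + 1/25.
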